Interventions and Duration

This is an open-label, single arm trial of orally-administered C7 in G1D. Subjects will replace a fixed percentage of their daily caloric intake (based on the results of Protocol 1) with C7 for 6 months, undergo full evaluation and discontinuation of treatment at a 6 month visit, and return for an off-treatment follow up visit 3 months after C7 oil discontinuation, for total duration of participation of 9 months. Subjects will undergo

treatment initiation on a 24-hour inpatient basis. During that 24-hr inpatient treatment initiation, subjects will have continuous EEG both to monitor for real-time seizure activity (for safety) and to determine EEG changes (secondary outcome) before, during, and after treatment initiation. Subjects will undergo clinical evaluation, comprehensive blood work, ataxia scale rating, EEG, and neuropsychological testing at baseline, 6 months, and 9 months.

Important: As described in the Proposal and in (1), C7 is always administered as a **replacement** (nor as a source of extra calories for an otherwise unchanged regular diet) to a fraction of the daily calories that are normally consumed by each subject via other nutrients. As such, there is **no caloric impact** of C7 (i.e., the calories that a subject will consume remain unchanged by the addition of C7 to the diet to replace other nutrients – predominantly fat).

Sample Size and Population

Forty-five subjects receiving no dietary therapy (i.e., consuming a normal diet) with a proven (genetically determined) G1D diagnosis will be enrolled. Subjects may be male or female, between the ages of 2 and 35 years old (N=15 per age group: 2 to 6, 7-11, and 12-35 years old), and must be willing to provide assent if they are of age 10-17. Subjects may be English or Spanish speaking. Subjects may be currently taking anticonvulsants or other medications. Subjects must agree not to change their dietary therapy during the trial without consulting with the study team. Subjects must have evidence of abnormal EEG in the last 36 months.

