3. STUDY DESIGN

This is an open-label, phase II trial of C7 in subjects with G1D.

Forty-five subjects with G1D receiving a modified atkins diet or a normal diet will be enrolled. Subjects will undergo all baseline and follow-up clinic procedures in the Neurology Outpatient Clinic located in the Children's Medical Center Ambulatory Care Pavilion. Inpatient procedures including blood draws will be completed in the Children's Medical Center Epilepsy Monitoring Unit (EMU). These facilities can accept adults as well as children subjects.

Evaluation of outcome measures will be accomplished at the pre- and post-baseline assessments, 6 month post-treatment and 9 month off-treatment time points by comparing baseline, post-treatment, and endpoint measures. Analyses of changes in comprehensive blood work and side effects over time will help ensure further safety and tolerability of C7 oil at the specified dose; improvement in ataxia rating scale, EEG, clinical evaluation, and neuropsychological testing will confirm the use of the clinical measures to assess outcomes.

Neuropsychological testing at the 6-month time point is designed to capture changes in neuropsychological functioning secondary to oil treatment. Testing again at the 9-month time point is designed to assess whether those changes persist for at least the short term (3 months after discontinuation of C7 oil). Most of the measures have alternate forms that may be utilized to minimize practice effects between the 6-month and 9-month time points, or they have shown not to demonstrate practice effects over a 3-month timeframe. As the IQ measures do not have alternate forms and likely are more sensitive to practice effects over that 3-month timeframe, we will not be conducting a 6-month administration of those measures in order to obtain an optimally valid estimate of intellectual functioning at the 9-month time point.

To address the potential circumstance that C7 may be associated or coincide with an increase in clinical seizure frequency between visits, an additional optional procedure will include the performance of a routine outpatient clinical EEG. This procedure will be obtained and reported locally (i.e., in the area of patient residence) in an accredited clinical facility and the report forwarded to the M.D. investigators for decision and intervention as detailed below.

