9. STATISTICAL CONSIDERATIONS

9.1. General Design Issues

In the proposed single-arm phase II trial, we define favorable impact on the neurocognitive outcome as at least 0.5 standard deviation (SD) improvement in performance on attention measures (measured as described above) after administration of C7. That is, impact on the outcome is determined by whether a treatment causes at least 0.5 SD improvement on the primary attention measure for that age group in a single arm trial and the interest is **primarily focused on reaching a decision on whether to progress with C7 to a future larger trial**. (Note: The SD is a normative parameter provided with the testing instruments). The evidence to make this decision is evaluated by testing the null hypothesis that the true efficacy rate is less than or equal to some pre-specified value. It is desirable to achieve this goal whilst minimizing the number of subjects exposed to a novel agent. Here, we use the Simon's optimal two-stage design that yields the smallest expected sample size when the null hypothesis is true.

We apply Simon's optimal two-stage design (24) using as primary outcome attention performance for each of three age groups. At least 0.5 SD improvement in performance on the primary attention measure after the administration of C7 is considered a favorable outcome. The measurement of 0.5 SD improvement is commonly accepted as the cutoff for a minimally clinically important difference, as described in various studies (e.g., 32, 33).

This protocol will yield data that allow a clear **go/ no-go decision** regarding whether C7 should proceed to an efficacy trial:

- If a favorable outcome occurs in less than 50% of subjects, we will recommend that C7 not proceed to an efficacy trial.
- If a favorable outcome occurs in at least 80% of subjects, we will recommend that C7 proceed to an efficacy trial.

The sample size estimation for this optimal two-stage design is given in Section 9.3.

If an intermediate number of subjects (51 – 79%) exhibit a favorable primary attention outcome, the rest of outcomes, including the long-term, 6-month responses, will be considered for the go/ no-go decision on the basis of impact on these outcomes and the disease process, in addition to tolerability and safety indicators.

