Although a variety of designs were considered, including crossover designs for non-ketogenic diet subjects and randomization to C7 or ketogenic diet, several factors contributed to the development of an open-label design. The G1D population, while hypothesized to be greater than previously realized, is currently a relatively small population and the number of patients needed to adequately power a cross over study could be difficult to recruit. This holds true for a head to head comparison of C7 and ketogenic diet, although the increasing availability of genomic testing may increase the available population in the next few years. Finally, and most importantly, the safety and tolerability of C7 has not been rigorously proven in G1D. Therefore, this issue needs to be addressed before entering into advanced clinical trials.

A six-month, on-supplement follow up time period was chosen in order to provide long-term safety and tolerability data for triheptanoin. Additionally, we consulted with [name] (co-investigator), an established pediatric neuropsychologist expert in G1D. It is general practice to wait a minimum of 6 months after ischemic insult to the brain (such as traumatic brain injury or stroke) before assessing neurocognitive changes. This time period is consistent with how long it takes the brain to demonstrate performance improvement after these insults. Because chronic seizures can also induce long-term brain changes, 6 months was chosen to allow sufficient time for the brain to exhibit improvement that could be captured by the outcome measure tools.

The three-month exit visit allows us to assess whether changes in brain wave activity and other neurocognitive measures persist after withdrawal of oil.

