9.2. Outcomes

9.2.1. Primary outcome

9.2.1.1. Attention performance

C7 provides a spectrum of short-term (hours to days) and long-term (over 6 months) benefits in subjects with G1D as measured by a 0.5 SD improvement in performance on the primary attention measure both in the acute and long-term.

Subjects receiving C7 supplementation will experience a significant (0.5 SD) improvement in performance on the primary attention measure for each subject's age group.

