9.3. Sample Size and Accrual

We estimated the sample size using the primary outcome (attention) for each of three age groups. The same method will be applied for sample size estimation in each of three age groups. An improvement of 0.5 SD or more on the primary attention measure

after the administration of C7 is considered a favorable outcome. This study will yield data that allow a clear go/no-go decision regarding whether C7 should proceed to an efficacy trial: If a favorable outcome occurs in less than 50% of subjects, we will recommend that C7 not proceed to an efficacy trial. If a favorable outcome occurs in at least 80% of subjects, we will recommend that C7 proceed to an efficacy trial.

The sample size was estimated using Simon's optimal two-stage design (24). The null hypothesis that the proportion of favorable outcome is 50% will be tested against a one-sided alternative hypothesis that the proportion of favorable outcome is 80%. In the first stage, 7 subjects will be accrued. If there are 4 or fewer favorable outcomes in these 7 subjects, the study will be stopped, and we will recommend that C7 not proceed to an efficacy trial. Otherwise, 6 additional subjects will be accrued for a total of 13 subjects. If 8 or fewer favorable outcomes are observed in 13 subjects by the end of stage two, then no further investigation of C7 is warranted. This design yields a type I error rate of 0.1 and power of 80% when the true favorable outcome occurs in 80% of subjects. We plan to recruit 15 subjects with an expected 15% dropout rate resulting in 13 subjects for each age group. That is, we will recruit a total of 45 subjects for this protocol.

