9.5. Data Analyses

Summary descriptive statistics: For normally distributed, continuous data, means and standard deviations will be used to describe the demographic and clinical characteristics of the patient population participating in the study and medians and semi-interquartile ranges will be used to describe characteristics of the patient population when the data are continuous, non-normally distributed. For categorical or dichotomous variables, the frequency or the proportion will be reported.

Primary Aim: The primary aim is demonstrating the benefit of C7, as measured by a change in performance on the primary attention measure for each age group. The proportion of subjects who achieved favorable outcome will be estimated along with the corresponding 95% confidence interval using an exact binomial method. We will also investigate if there will be significant differences in the proportions of favorable outcomes among three age groups using Fisher's exact test. We will make every effort to minimize the missing data. We expect minimal amount of missing data. If missing data occurs, missing data will be imputed using multiple imputation techniques.

Generalized estimating equation (GEE) analysis will be used to examine if C7 positively affects other neuropsychological (e.g., IQ, language, processing speed) and neurological performance, such as ataxia over time (baseline, 6 months, and 9 months).

Secondary Aim: A secondary aim is to evaluate the effect of C7 supplementation of a regular diet on an EEG activity and to evaluate the safety of C7 supplementation. EEG will be analyzed in 3 ways (spike-wave duration, total number of seizures and background of the EEG as described above). GEE analysis will be used to examine if there are significant changes in EEG activity and safety over time. GEE analysis will be also conducted to investigate whether attention neuropsychological scores correlate with the EEG findings.

Study end. Statistical analyses at the end of the study will examine the initial measures at baseline, 6 months, and 9 months. Repeated measurement data will be analyzed using the generalized estimating equation (GEE) approach. The GEE method has been widely used for the analysis of repeated measurement data because of its robustness to random missing and misspecification of the true correlation structure.

SAS V9.4 (SAS Institute, Inc. SAS V9.4, Cary, NC, 2014) will be used to analyze the data.

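### The plan does not say which visit decides a favorable attention outcome, and its sections point to different visits

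*Combined protocol and SAP*

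**What the plan says.** Section 9.1 defines the response: "At least 0.5 SD improvement in performance on the primary attention measure after the administration of C7 is considered a favorable outcome". Section 9.3 repeats it with the same open timing and applies Simon's two-stage rule to it in each of three age groups.

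The Schedule of Neuropsychological Testing in 6.3.9 gives both primary measures (the continuous performance test, and the Working Memory Index for the youngest group) four times: before oil on Visit 1 Day 1, on oil on Visit 1 Day 2, on oil at 6 months, and off oil at 9 months. Two on-oil tests therefore fit the definition.

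The texts that bear on the choice are these:

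- **Acute, by implication.** For an intermediate response rate, 9.1 says "the rest of outcomes, including the long-term, 6-month responses, will be considered for the go/ no-go decision". If the 6-month responses belong to the remaining outcomes, the deciding result must be the earlier one.
- **Both times.** Section 9.2.1.1, under the primary outcome heading, speaks of "0.5 SD improvement in performance on the primary attention measure both in the acute and long-term".
- **6 months.** Section 3 says "Neuropsychological testing at the 6-month time point is designed to capture changes in neuropsychological functioning secondary to oil treatment". The design rationale in 9.1 says "6 months was chosen to allow sufficient time for the brain to exhibit improvement that could be captured by the outcome measure tools".
- **No visit.** The Primary Aim paragraph of 9.5 describes the exact binomial estimate without naming a visit. The list later in 9.5, "Statistical analyses at the end of the study will examine the initial measures at baseline, 6 months, and 9 months", belongs to the end-of-study repeated-measures analysis.

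**The concern.** A two-stage binomial rule controls error for one yes/no response per subject, defined before the data are seen. Here the text supports three definitions of that response: Day 2, 6 months, or both. They are not interchangeable. Requiring both visits makes a favorable result harder to reach and lowers the power. Leaving the visit open until results are known allows the better one to be used, which raises the chance of passing when C7 does not help.

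The trial is open-label and single-arm, and 9.1 says its main interest is the decision on a larger trial, so fixing the response in advance is a main safeguard.

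The stage 1 stop depends on the same choice. With Day 2, the seventh result in an age group is known at once. With 6 months it comes half a year later, while enrollment may continue.

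**Working it through.** **Inputs.** From 9.3: null rate 0.50, alternative 0.80, stop at 4 or fewer of 7, fail at 8 or fewer of 13, error 0.1, power 80%. From 9.1: a direct go recommendation needs at least 80% favorable. From 4.3.2: 1-2 subjects enrolled per month. The documents give no correlation between a subject's Day 2 and 6-month responses, so it is assumed and varied.

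**1. The plan's own figures, one fixed visit.** The chance of passing is the sum over x = 5, 6, 7 of P(x of 7) × P(at least 9 − x of the next 6).

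- Rate 0.50: 0.1641 × 0.3438 + 0.0547 × 0.6563 + 0.0078 × 0.8906 = 0.099.
- Rate 0.80: 0.2753 × 0.9011 + 0.3670 × 0.9830 + 0.2097 × 0.9984 = 0.818.

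The stated 0.1 and 80% are reproduced. The design is sound once a visit is named.

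**2. An anchor for the correlation.** Let Y0 be the baseline test and Y1, Y2 the two later tests, with equal variance s² and equal retest correlation r. Then Cov(Y1 − Y0, Y2 − Y0) = s²(1 − r), and each change has variance 2s²(1 − r). The correlation is (1 − r) / [2(1 − r)] = 0.5 for any r below 1. This is a reference value, not an estimate for this population.

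**3. Both visits required, true rate 0.80 at each.** P(both) comes from a bivariate normal model and is put into the formula of step 1.

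| Assumed correlation | P(favorable at both) | Chance of passing |
|---|---|---|
| 0 | 0.640 | 0.38 |
| 0.5 | 0.687 | 0.51 |
| 0.9 | 0.750 | 0.69 |
| 1 (full agreement) | 0.800 | 0.818 |

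**4. Better visit chosen after the results, true rate 0.50 at each, rule applied to each visit.**

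- Independent: 1 − (1 − 0.0992)² = 0.189.
- Correlation 0.5: 0.175 (simulation).
- Full agreement: 0.099.

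**5. The same for a direct go.** Since 10/13 = 76.9% and 11/13 = 84.6%, the 80% threshold needs 11 of 13. With stage 1 passed and a true rate of 0.50, one fixed visit gives 0.011. The better of two gives 1 − (1 − 0.0112)² = 0.022 if independent, and also about 0.022 at correlation 0.5.

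**6. Stage 1 timing.** If enrollment is spread evenly, 1-2 per month over three groups is 0.33-0.67 per group per month. Over 6 months that is 2-4 more subjects per group before a 6-month stage 1 result could be read.

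**The case against.** Several points on the other side stand.

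- Section 9.1 never mentions Day 2. It points there only by how it classes the 6-month responses.
- The visit list in 9.5, and the synopsis line on "neuropsychological testing at baseline, 6 months, and 9 months", do not define the binomial response. A reader might take them as designating 6 months. The first belongs to the repeated-measures analyses, and the second is a general outline that the detailed schedule extends with Day 2.
- Section 9.2.1.1 can be read as a statement of expected benefit. The EEG outcome in 9.2.2.1 is worded in the same way, and the next sentence of 9.2.1.1 repeats the 0.5 SD criterion with no timing. It need not be a both-visits rule. Still, it is the only timing given under the primary outcome heading.
- A reader might infer that the chance of a wrong go recommendation rises to 17-19%. It does not: that is the chance of passing 8 of 13. With 9 or 10 of 13 (69-77%), 9.1 calls for weighing the other outcomes, safety and tolerability.
- A reader might infer that a subject could count by improving at either visit. No text proposes this.
- A reader might infer that 6 months is plainly what was meant. The rationale in 9.1 gives long-term safety and tolerability first as the reason for 6 months. Section 3 contrasts 6 with 9 months and also lists assessments just before and after baseline. The dropout allowance ("We plan to recruit 15 subjects with an expected 15% dropout rate resulting in 13 subjects for each age group") says nothing on timing. Within the decision rule itself, the 6-month responses are supporting evidence.

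Part of the text between 9.3 and 9.5 was not available for this review, so the absence of a named visit is established only for the rest. None of this supplies the missing visit or reconciles 9.1 with 9.2.1.1.

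**Conclusion.** The point holds: in the text available, the deciding visit is not named, and the sections that bear on it conflict. This is more than a missing detail, because the error and power stated in 9.3 depend on the answer.

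With one named visit they hold (0.099 and 0.818). If 9.2.1.1 is applied literally, power falls to 0.38-0.69 for correlations from 0 to 0.9, and to 0.51 at 0.5. If the better visit is taken afterwards, the chance of passing at a true 50% rate is 0.175-0.189 for correlations from 0.5 to 0, and the chance of a direct go is about 2% instead of 1.1%.

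These figures assume the same true rate at both visits and a bivariate normal link between them. They shrink as the visits agree more closely and vanish at full agreement. They show what the open choice can do. They are not evidence that the sponsor intends to choose after seeing results, nor that either visit is the wrong one.

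**What to change.** Name one deciding visit, measured from the pre-oil test on Visit 1 Day 1, in the same words in 9.1, 9.2.1.1, 9.3 and the Primary Aim paragraph of 9.5. Make the other visit secondary. The choice is the sponsor's.

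- **If Day 2:** keep the 9.1 sentence on the remaining outcomes, and move the long-term part of 9.2.1.1 to 9.2.2.
- **If 6 months:** change that 9.1 sentence so that it refers to the acute Day 2 response instead of the 6-month responses, and move the acute part of 9.2.1.1 to 9.2.2.

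In either case, state in 9.3 that stage 1 is decided on the first seven evaluable results at the named visit in each age group.

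**Cost.** No new visit or test is needed. With Day 2 the change is wording only. With 6 months, the stage 1 result comes about half a year later and may use some or all of the 6-month enrollment reserve in 4.3.2 (months 45-50).

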9.2. Outcomes

9.2.1. Primary outcome

9.2.1.1. Attention performance

C7 provides a spectrum of short-term (hours to days) and long-term (over 6 months) benefits in subjects with G1D as measured by a 0.5 SD improvement in performance on the primary attention measure both in the acute and long-term.

Subjects receiving C7 supplementation will experience a significant (0.5 SD) improvement in performance on the primary attention measure for each subject's age group.

9.2.2. Secondary outcomes

9.2.2.1. EEG

C7 provides a spectrum of short-term (hours to days) and long-term (over 6 months) benefits in subjects with G1D as measured by a decrease in abnormal EEG activities as defined above both in the acute and long-term.

9.2.2.2. Other neuropsychological and neurological performance, such as ataxia.

Subjects undergoing C7 supplementation will experience improvements in neuropsychological and neurological performance over the long term. Subjects will experience an increase in vocabulary expression and recall in both the acute (days) and long term (months) time frames. Subjects will also experience decreases in ataxia and other neurological symptoms measured on the neurological assessment.

9.2.2.3. Safety

C7 supplementation is safe when used over the long term (6 months) period. Subjects will experience no clinically significant changes in standard laboratory measures (blood cell count, blood electrolytes, AST, ALT, blood urea nitrogen, creatinine, lipid panel, plasma glucose and beta-hydroxybutyric acid.) and exhibit no evidence of toxicity as measured by the VA Toxicity Scale.

9.3. Sample Size and Accrual

We estimated the sample size using the primary outcome (attention) for each of three age groups. The same method will be applied for sample size estimation in each of three age groups. An improvement of 0.5 SD or more on the primary attention measure

after the administration of C7 is considered a favorable outcome. This study will yield data that allow a clear go/no-go decision regarding whether C7 should proceed to an efficacy trial: If a favorable outcome occurs in less than 50% of subjects, we will recommend that C7 not proceed to an efficacy trial. If a favorable outcome occurs in at least 80% of subjects, we will recommend that C7 proceed to an efficacy trial.

The sample size was estimated using Simon's optimal two-stage design (24). The null hypothesis that the proportion of favorable outcome is 50% will be tested against a one-sided alternative hypothesis that the proportion of favorable outcome is 80%. In the first stage, 7 subjects will be accrued. If there are 4 or fewer favorable outcomes in these 7 subjects, the study will be stopped, and we will recommend that C7 not proceed to an efficacy trial. Otherwise, 6 additional subjects will be accrued for a total of 13 subjects. If 8 or fewer favorable outcomes are observed in 13 subjects by the end of stage two, then no further investigation of C7 is warranted. This design yields a type I error rate of 0.1 and power of 80% when the true favorable outcome occurs in 80% of subjects. We plan to recruit 15 subjects with an expected 15% dropout rate resulting in 13 subjects for each age group. That is, we will recruit a total of 45 subjects for this protocol.

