Clinical significance and meaningfulness of the primary neurocognitive (attention) outcome: Attention is a core cognitive function that permits access to other areas of cognition and is commonly impaired in association with seizure disorders. Existing research has indicated that dietary interventions have the potential to promote attention functioning in children with G1D (26, 27). With regard to long-term outcomes, research in the field of childhood absence epilepsy has shown that even after attaining seizure freedom, attention deficits may remain (28). In other words, even normal EEG findings may not correspond to functional neuropsychological improvements. These findings in the field of childhood absence epilepsy are significant for the present study given that EEG seizures are more common than observable seizures in children with G1D. Additionally, these findings with regard to childhood absence epilepsy may help explain why language functioning improvements in children with G1D after administration of triheptanoin were not statistically significant in a previous trial (1). Again, attention is a core cognitive function that permits access to other areas of cognition (including language) and is commonly impaired in association with seizure disorders. For all of these reasons, attention functioning as measured by neuropsychological testing (described below in 6.3.9) may be a more relevant primary outcome for the present study than EEG findings. As noted above, the measurement of 0.5 SD improvement is commonly accepted as the cutoff for a minimally clinically important difference, as described in various studies (e.g., 32, 33), and thus in the present study we will look for this degree of improvement in performance on the primary measure of attention to answer the go/no-go decision for each age group.

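### Section 9 runs the Simon rule in each of three age groups but attaches its stop and recommendation to the whole study and to C7; the stated 10% error and 80% power hold per age group only.

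*Combined protocol and SAP*

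**What the plan says.** Sections 9.1 and 9.3 apply Simon's optimal two-stage design to each of three age groups. Each group recruits 15 subjects to yield 13, for 45 in total. The test is set out in 9.3: "The null hypothesis that the proportion of favorable outcome is 50" percent, against a "one-sided alternative hypothesis that the proportion of favorable outcome is 80" percent. "In the first stage, 7 subjects will be accrued", and with 4 or fewer favourable outcomes "the study will be stopped, and we will recommend that C7 not proceed to an efficacy trial". Otherwise 6 more are accrued, and 8 or fewer of 13 means that C7 is not pursued further. The section then states: "This design yields a type I error rate of 0.1 and power of 80" percent, at a true rate of 80%.

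The counts of 7 and 13 are thus counts for one age group, while the consequences are written for the study and for C7. Section 9.1 also words its recommendation for C7 as a whole: "If a favorable outcome occurs in at least 80% of subjects, we will recommend that C7 proceed to an efficacy trial", with no-go below 50% and a zone of 51–79% in which the other outcomes, tolerability and safety are weighed.

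A later paragraph of 9.1, on the clinical meaning of the attention outcome, says instead that the 0.5 SD criterion serves "to answer the go/no-go decision for each age group". Section 9.5 states the primary aim by age group, gives an exact 95% interval for the proportion, and compares the groups with Fisher's exact test. It gives no rule for combining them. The text between 9.3 and 9.5 was available only in part, so a rule placed there could not be checked.

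**The concern.** A stopping rule has to be executable. If one age group reaches 4 or fewer of 7, the text of 9.3 closes the trial, whereas 9.1 read by age group closes only that group. The investigator and the monitoring committee cannot tell which is meant. Unequal group results are plausible: the groups differ in age, and under 6.3.9 the youngest is judged on a working memory index while the other two are judged on a continuous performance test.

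The same gap affects the trial's stated main purpose, the decision whether to go on to a larger trial. If the way of combining three results is settled only once they are known, no error rate can be attached to that decision in advance.

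**Working it through.** **Inputs (9.1 and 9.3).** Null rate 0.50; alternative 0.80, one-sided; stop at 4 or fewer of 7; success at 9 or more of 13; design applied in three age groups. Independence between groups is an assumption made here.

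**Step 1: reproduce the plan's figures for one group.** A group succeeds if stage 1 gives x = 5, 6 or 7 and stage 2 (6 subjects) supplies at least 9 − x more:

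P(success | p) = Σ P(X₁ = x; 7, p) × P(X₂ ≥ 9 − x; 6, p)

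- p = 0.5: 0.1641 × 0.3438 + 0.0547 × 0.6563 + 0.0078 × 0.8906 = 0.0992.
- p = 0.8: 0.2753 × 0.9011 + 0.3670 × 0.9830 + 0.2097 × 0.9984 = 0.8182.
- Stage 1 stop, P(X₁ ≤ 4): 0.7734 at p = 0.5 and 0.1480 at p = 0.8.

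The stated 0.1 and 80% are confirmed for one group. An exhaustive search also confirms 4/7, 8/13 as the optimal design for these requirements.

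**Step 2: a study-level stop, taken literally.** The study stops if any group has 4 or fewer of 7.

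- All groups at 80%: 1 − (1 − 0.1480)³ = 1 − 0.6184 = 38.2%, against 14.8% for one group.
- Two groups at 80%, one at 50%: 1 − 0.8520² × 0.2266 = 83.6%.
- Power for a given group, if both other groups' stage 1 results arrive before it finishes: 0.8182 × 0.8520² = 59.4%. This is the lower limit; a group that finishes first keeps its 81.8%.

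**Step 3: one recommendation on C7 from three groups.** The plan states none of these rules. They show the range. With a = 0.0992 or 0.8182, the formulas are 1 − (1 − a)³, 3a²(1 − a) + a³ and a³.

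| Rule for a go on C7 | False go, all at 50% | Power, all at 80% |
|---|---|---|
| Any group succeeds | 26.9% | 99.4% |
| At least 2 of 3 succeed | 2.8% | 91.3% |
| All three succeed | 0.1% | 54.8% |

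None of them gives 10% and 80%.

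**Step 4: the percentage cut-offs in 9.1.** Simon success begins at 9/13 = 69.2%. The 80% go rule needs 0.80 × 13 = 10.4, so 11 of 13 (84.6%).

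- 9/13 (69.2%) and 10/13 (76.9%) pass Simon but fall in the 51–79% zone.
- 7/13 (53.8%) and 8/13 (61.5%) fail Simon but fall in the same zone, as does 4/7 (57.1%), which stops at stage 1.

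If a go strictly required 11 of 13 after passing stage 1, the per-group figures would be:

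- p = 0.5: 0.1641 × 0.0156 + 0.0547 × 0.1094 + 0.0078 × 0.3438 = 0.0112.
- p = 0.8: 0.2753 × 0.2621 + 0.3670 × 0.6554 + 0.2097 × 0.9011 = 0.5017.

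That is an error of 1.1% and power of 50.2%.

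**The case against.** The strongest reply is that the plan mostly points to decisions by age group. Sections 9.1, 9.3 and 9.5 all name the age group, and the sentence about stopping the study sits inside a description of one group's 7 and 13 subjects. It may be standard Simon wording that was not adapted. On that reading 0.099 and 0.818 are correct for every decision taken. This stands. A reader might infer that the stated 10% and 80% are wrong; the documents do not support that, because the figures are right for each group's test.

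Second, a reader might infer that the trial runs a 27% false-go risk or has only 55% power. Those figures belong to rules under which any one group suffices or all three must succeed, and the plan states neither. With decisions by group, 27% is the chance of at least one error across three separate screening questions. Reporting it is useful disclosure, but it does not show that the design fails.

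Third, a reader might infer that a literal stop cuts every group's power to 59%. That holds only for a group still open when both other stage 1 results are in. Section 4.3.2 expects 1–2 subjects a month and gives no order by age group, so the loss is a worst case.

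What the reply does not remove is the conflict in the text. The consequence in 9.3 is stated explicitly for the study and for C7, and it differs from the decision by age group in 9.1. This is a stated rule at odds with another part of the plan, not merely an omitted detail.

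**Conclusion.** The level of the decision is inconsistent between 9.3, together with the recommendation wording in 9.1, and the paragraph of 9.1 that places the decision in each age group. The error of 0.1 and power of 80% are correct per age group and should be kept as such. They do not carry over to a study-level stop or to one recommendation on C7.

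The largest practical consequence is that the literal rule would stop a trial in which C7 works at 80% in every group with probability 38.2%. The quoted error rates also apply only to the Simon cut-off of 9 of 13, not to the 80% go rule or the discretionary zone.

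The combined figures rest on independent groups and on the true rates named in each scenario. The conclusion that no combination rule exists is limited to the text available, since part of the text between 9.3 and 9.5 could not be seen.

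**What to change.** In 9.1 and 9.3:

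1. State that 4 or fewer favourable outcomes among the first 7 subjects of an age group stops accrual to that age group, and that the go/no-go recommendation on C7 is made for that age group. This adopts the reading 9.1 already contains.
2. Label 0.10 and 80% as per age group.
3. Add that, under the Simon rule and with independent groups, the chance of at least one false go is about 27% if all groups are at 50%, and the chance that all three succeed is about 55% if all are at 80%.
4. Reconcile the Simon cut-off (9 of 13) with the 80% and 50% recommendation limits and the 51–79% zone, so that each possible count leads to one outcome. If the go criterion is not 9 of 13, replace the error and power figures, including those in item 3, with the ones that belong to it.

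Items 1 to 3 change wording only: the 4/7, 8/13 bounds and the 45 subjects stay as they are. The cost is that a less favourable overall figure (27%) is disclosed. Item 4 needs a decision by the sponsor but no added subjects if 9 of 13 is kept.
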